Does Adding Lidocaine to Corticosteroid Injections Reduce Pain Intensity in Hand Surgery?

Date: 7-18-2019

Hypotheses

Primary null hypothesis:

There is a difference in pain intensity during injection (directly assessed after the injection) between patients receiving corticosteroid injections in combination with lidocaine vs without lidocaine, for any hand/wrist injection.

Secondary hypotheses:

- There is a difference in pain intensity 4 hours after injection between patients receiving corticosteroid injections in combination with lidocaine vs without lidocaine, for any hand/wrist injection.

As per some previous studies we will perform our other analyses based on superiority, without margins of non-inferiority, as this is only relevant for the analysis of the primary outcome.

 There are no factors (including adding lido to corticosteroid injection) independently associated with pain intensity, satisfaction with the visit, and perceived empathy.

Background and significance

In patients with carpal tunnel syndrome, injection of glucocorticoids into the region of the carpal tunnel is intended to reduce tissue inflammation and aid recovery. [3] For trigger finger and de Quervain tendinopathy, glucocorticosteroid injection can cure the problem. [4;8] The corticosteroid injection is usually mixed with lidocaine. [3;4] Lidocaine is a local anesthetic commonly used in clinics and it is characterized by a rapid onset of action. [1]

In case of trigger finger, a systematic review including two randomized trials, found that glucocorticosteroid injection was more effective for symptom relief than lidocaine injection alone. [5;6]. Dernek et al. shows no difference in efficacy between treatment for carpal tunnel syndrome with lidocaine and treatment with corticosteroid. [2] There's a lack of evidence about the use of lidocaine injection as an addition to steroids against pain during injections.

The average pain caused by corticosteroid injection for trigger finger is 4.3 on a scale of 10 when given with lidocaine. [7] Among other things, pain is correlated with expected pain, heightened illness concern, pain catastrophizing and depression, but not with prior injection or technique. [7] Adding lidocaine adds to the volume of the injection, which might increase pain. It's possible that injecting cortisone without any lidocaine would be more comfortable than with lidocaine.

The aim of this randomized controlled trial is to assess the difference in pain intensity between patients receiving a corticosteroid injection with or without lidocaine in patients with a hand condition. Secondarily, the aim of this study is to assess factors independently associated with pain intensity, satisfaction with the visit, and perceived empathy.

Proposed methods

Study design: Randomized Controlled Trial Recruitment methods (if applicable):

All patients offered a corticosteroid injection will be invited to enroll in the middle of their visit prior to injection. A research assistant will obtain informed consent. Patients will be randomized, using a random number generator in Microsoft Excel, in two groups for the corticosteroid injection, one group with lidocaine and one group without lidocaine. Then the surgeon will give the corticosteroid injection. The group without the lidocaine will get an injection with only steroids. To make this a double-blind study, the medical assistant will put a piece of tape around the syringe to cover up the volume.

Data will be recorded on tablets using HIPAA compliant REDCap. After the injection, patients will be asked to complete a survey on REDCap in the following order: demographics, prior steroid injection, pain intensity, patient satisfaction with the visit, JSPPPE, PCS-4, PHQ-2, and PSEQ-2. This will take the patients 5 minutes to complete. A research assistant will ask the surgeon for the diagnosis, initial treatment, approach of injection and intrasheath or extrasheath injection. The medical assistant will complete the use of lidocaine in addition to corticosteroid injection, any other added substances and the volume of the injection.

After 4 hours, the research assistant will do the follow up call and ask for the pain intensity.

Inclusion Criteria:

- All patients offered a steroid injection in a hand surgeon's office
- Aged 18-89 years
- English speaking patients
- Able to provide informed consent

Exclusion criteria:

- Non-English/Spanish speakers

Measured variables

Response variables:

-

- Pain intensity in the last 7 days
 - \circ $\,$ 11-point ordinal scale, with 0 for no pain at all and 10 for worst pain ever
- Pain intensity during injection
 - \circ 11-point ordinal scale, with 0 for no pain at all and 10 for worst pain ever
 - Pain intensity 5 minutes after injection
 - \circ 11-point ordinal scale, with 0 for no pain at all and 10 for worst pain ever
- Pain intensity 4 hours after injection
 - \circ $\,$ 11-point ordinal scale, with 0 for no pain at all and 10 for worst pain ever
- Patient satisfaction with the visit, direct after visit and after 4 hours
 - 11-point ordinal scale, with 0 for not satisfied at all and 10 for most satisfied)
- Perceived empathy

o **JSPPPE**

Explanatory variables:

- Use of lidocaine in addition to corticosteroid (Yes / No)
- Total volume of injection
- Approach of injection
- Intrasheath or extrasheath injection
- Diagnosis
- Initial treatment
- Prior steroid injection anywhere
 - Prior steroid injection at that site
- Abbreviated Pain Catastrophizing Scale (PCS 4)
- Patient Health Questionnaire (PHQ 2)
- Pain Self-efficacy Questionnaire (PSEQ 2)
- Patient demographics
 - o Sex (female, male)
 - Age (text)
 - Race/ethnicity (1. White, 2. Black/African American, 3. Latino, 4. Other.
 - Marital status (1. Married/Unmarried Couple, 2. Divorced/Separated, 3. Widowed, 4. Single.)
 - Level of education (1. High school or less, 3. 2-year college, 4. 4-year college, 5. Post-college graduate degree)
 - Work status 1. Employed, 2. Out of Work, 3. Unable to Work, 4. Retired)
 - Insurance status (1. Medicare/Medicaid, 2. Commercial, 3. Uninsured, 4. Worker compensation, 5. Other)

Statistical analysis

Intention to treat analysis may bias a non-inferiority trial towards finding no difference. Therefore, we will perform both an intention to treat and per protocol analysis.

Primary and secondary null hypothesis

Unpaired t-test for hypothesis testing and MV linear regressions for other hypotheses.

A priori power analysis

The primary outcome will be the difference in pain immediately after the injection after randomization between corticosteroid shots without lidocaine compared with adding lidocaine.

We aim to assess the non-inferiority of corticosteroid shots without lidocaine compared with adding lidocaine. The difference in pain score will be compared by unpaired t-test. We will also report the mean, with SD and 95% CI and the mean difference with 95% confidence interval. We anticipate a mean pain score of 8.0 (95% CI 7.6 to 8.4) with a standard deviation of 1 for the shots with lidocaine. Non-inferiority will be considered if

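### The post-injection survey places one undefined pain entry after demographics and injection history, although the primary pain score is to be taken directly after the injection; the delay is avoidable and may affect only the lidocaine arm.

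*Combined protocol and SAP*

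**What the plan says.** Under Hypotheses, the primary outcome is "pain intensity during injection (directly assessed after the injection"). Under A priori power analysis the wording changes: "The primary outcome will be the difference in pain immediately after the injection".

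Under Proposed methods (Recruitment methods), patients are asked after the injection to "complete a survey on REDCap in the following order: demographics, prior steroid injection, pain intensity", followed by satisfaction, JSPPPE, PCS-4, PHQ-2 and PSEQ-2. Of the whole survey the plan says: "This will take the patients 5 minutes to complete". The time from injection to the start of the survey is not stated.

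The response variables under Measured variables include "Pain intensity during injection", a separate rating 5 minutes after the injection, a rating for the previous 7 days, and one at 4 hours. The 4-hour rating is collected by telephone. The survey order has one pain entry for the other three.

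Under Background and significance, lidocaine is "characterized by a rapid onset of action". Only one arm receives it; the other is given steroid alone.

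**The concern.** The primary score is meant to be taken at once, yet the stated procedure puts background questions first. Those questions do not depend on the injection and could be asked at another time.

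A delay common to both arms would mostly add noise. This one need not act equally, because a fast-acting anaesthetic is present in one arm while the questions are being answered. Randomisation and the taped syringe do not remove such an effect, since it arises from when the outcome is measured.

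The survey also leaves open which pain is recorded. Pain during injection and pain 5 minutes later are separate variables in the plan, and a late or loosely worded rating blurs them. At stake is whether the primary comparison measures the pain of the injection or partly the numbness that follows, tested against a margin of only 0.5 points on a 0 to 10 scale.

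**Working it through.** **1. Position of the primary item.** The variable list gives seven demographic items (sex, age, race/ethnicity, marital status, education, work status, insurance) and two prior-injection items (anywhere, and at that site). Items before the pain entry: 7 + 2 = 9. The plan describes no earlier rating by staff, no maximum interval and no time stamp.

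**2. Possible delay (assumed, for scale only).** Count three pain items, one satisfaction item, 4 + 2 + 2 items for PCS-4, PHQ-2 and PSEQ-2 (taken from their names), and 5 to 10 JSPPPE items, a number the documents do not give. The total is 9 + 3 + 1 + 8 + (5 to 10) = 26 to 31. With equal time per item in a 5-minute survey:

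- 9/31 × 5 = 1.45 minutes
- 9/26 × 5 = 1.73 minutes

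This excludes any gap before the survey starts. Equal time per item is an assumption, and simple demographic items may be quicker.

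**3. What the delay could do.** The documents give no onset time in minutes and no wording for the pain question, so there are two cases:

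- The item asks about current pain, as the power section's wording suggests. Onset before the rating then lowers the lidocaine-arm score directly.
- The item asks about pain during the injection, as in the hypothesis and the variable list. The event is over, and later numbness can act only through recall.

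**4. The plan's sample size.** Margin 0.5, SD 1, true difference 0, one-sided alpha 0.05, power 90%:

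n per group = 2 × [(1.645 + 1.282) × 1 / 0.5]² = 68.5, rounded up to 69, or 138 in total. This agrees with the plan.

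**5. Sensitivity to an assumed shift b in the lidocaine arm only.** The standard error of the difference is √(2/69) = 0.170. If non-inferiority means that the score without lidocaine is not worse by 0.5, the distance to the margin is 0.5 − b. The noncentrality is (0.5 − b)/0.170, and power comes from the noncentral t distribution with 136 degrees of freedom.

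| Assumed b (points) | (0.5 − b)/0.170 | Power |
|---|---|---|
| 0 | 2.94 | 90% |
| 0.05 | 2.64 | 84% |
| 0.1 | 2.35 | 76% |
| 0.2 | 1.76 | 54% |

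None of the non-zero values of b comes from the documents.

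**6. Dependence on the margin's direction.** The power section states the margin as no more than 0.5 points lower without lidocaine, although a higher score is worse. Taken literally, the distance becomes 0.5 + b, and the same shift makes the criterion easier to meet: at b = 0.1, power is about 97%.

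**The case against.** The strongest reply is that the primary item, as the hypothesis and variable list word it, concerns a completed event. Numbness a minute or two later need not change how a patient rates the needle, and the plan has a separate item for later pain. If current pain is meant instead, early anaesthesia is arguably part of the lidocaine effect under comparison. Neither timing word is defined in minutes, and a rating within a 5-minute survey may fairly count as directly after, especially beside a 4-hour call. The delay and the shifts are assumed, and any shift in one arm would give the same power figures whatever its cause.

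Much of this stands. A reader might infer that the primary score is known to mix injection pain with anaesthesia, that the test is biased against non-inferiority, and that power falls to 54%. The documents support none of these as fact. They give neither an onset time nor a size of shift, the recall wording weakens the mechanism, and the direction depends on how the margin is read.

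The objection does not explain why nine background items should come first, or which of three pain ratings the single entry records. If current pain immediately after injection is intended, delay changes which moment is measured. If pain during injection is intended, an early rating limits the influence of recall. An early, defined rating serves either reading.

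**Conclusion.** The point holds as a mismatch between procedure and outcome definition, with a possible arm-dependent measurement error of unknown size. Following the stated order postpones the primary rating behind nine items, and the entry is not tied to one of the pain variables listed.

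The 84% to 54% range shows only that a 0.5-point margin leaves little room for such an error. It assumes a lidocaine-arm shift of 0.05 to 0.2 points, SD 1, 69 per group, no true difference, and a margin meaning not worse by 0.5. The planned sample size reproduces and is unaffected. The direction of the margin is a separate matter to reconcile; the conflict over timing and item definition exists under either reading. The change is worth making because it is cheap and brings the procedure into line with the plan's own outcome, not because a bias of a given size has been shown.

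**What to change.** - Name the rating of pain during injection as the primary item, and use that wording in the hypothesis, the variable list, the survey and the power section.
- Make it the first survey item after the injection, with a REDCap time stamp so that the interval can be reported by arm.
- Move the demographic and prior-injection items to before the injection, since patients are enrolled before it, or to after the pain items.
- Record the 5-minute pain rating separately, at its own time.

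This adds no patients and no new outcome, and N stays at 138 before allowance for loss. It is slightly more than reordering a form: someone must present the first item promptly and the 5-minute item on time, and asking background items earlier shifts some work to before the injection.

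### As listed, the secondary regressions would adjust the lidocaine effect for three scales completed after the injection and for the injected volume

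*Combined protocol and SAP*

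**What the plan says.** Under Proposed methods, patients are "invited to enroll in the middle of their visit prior to injection", consent, are randomised and are then injected. The questionnaire comes next: "After the injection, patients will be asked to complete a survey on REDCap in the following order", namely "demographics, prior steroid injection, pain intensity, patient satisfaction with the visit, JSPPPE, PCS-4, PHQ-2, and PSEQ-2". The three psychological scales are therefore the last items, after the pain, satisfaction and JSPPPE ratings. No pre-injection administration is described, nor any instruction to answer for the time before the injection.

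The later contact is a telephone call: "After 4 hours, the research assistant will do the follow up call and ask for the pain intensity". The response variables also include "Patient satisfaction with the visit, direct after visit and after 4 hours".

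Under Explanatory variables, lidocaine (yes/no) stands beside "Total volume of injection", "Abbreviated Pain Catastrophizing Scale (PCS 4)", PHQ-2 and PSEQ-2. The matching secondary hypothesis begins "There are no factors (including adding lido to corticosteroid injection) independently associated with pain intensity" and goes on to satisfaction and perceived empathy. The Statistical analysis section assigns the t-test to hypothesis testing and multivariable linear regression to the other hypotheses. It does not say which variables enter which model.

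The Background section says that lidocaine makes the injected volume larger and that this might itself increase pain. The study design has the syringe taped so that its volume cannot be seen.

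**The concern.** A randomised comparison is protected by randomisation only while it is unadjusted or adjusted for variables that treatment could not have changed. Two kinds of listed variable fail that test.

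- **Total volume** is partly set by the arm. With volume in the model, the lidocaine coefficient describes lidocaine at equal volume, not the addition of lidocaine as the trial delivers it. It also removes the route by which the Background section suspects that lidocaine could hurt more. Because volume and arm are correlated, precision falls too.
- **The three scales** are answered after the injection and after it has been rated. A painful injection may shift a catastrophizing or self-efficacy score. If so, adjusting for the score removes part of any lidocaine effect.

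The same timing limits what the scale coefficients mean. For injection pain, immediate satisfaction and JSPPPE, the data cannot tell a trait that shapes the rating from a rating that shapes the score. For 4-hour pain and 4-hour satisfaction the scales come first, but they are still post-randomisation variables.

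At stake is the stated secondary aim. For pain, the regression would give a second lidocaine estimate that may differ from the t-test. For satisfaction and empathy, the regression appears to be the only planned source of a lidocaine estimate.

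**Working it through.** **Plan's own figure.** Margin 0.5, SD 1, one-sided alpha 0.05, power 90% (A priori power analysis): n per group = 2 × (1.645 + 1.282)² × 1² / 0.5² = 68.5, so 69 per group and 138 in total, as stated. This point does not change that figure.

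**Timing**

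1. Consent: before the injection, with no questionnaire.
2. Randomisation, then injection.
3. Survey: pain, satisfaction and JSPPPE (responses), then PCS-4, PHQ-2 and PSEQ-2 (explanatory).
4. Call at 4 hours.

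The three scales thus follow the randomised treatment for every outcome, and also follow the rating itself for the immediate outcomes.

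**Volume.** Inputs: 69 per arm and SD 1 (plan); arm difference in volume of D within-arm SDs (assumed). With equal arms, the share of volume variance due to arm is (D²/4)/(1 + D²/4), so the variance inflation for lidocaine is 1 + D²/4. Without volume, SE = √(2/69) = 0.170 and the 95% half-width is 1.978 × 0.170 = 0.34. This holds the residual SD at 1 and considers only arm and volume.

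| D | Variance inflation | SE | 95% half-width |
|---|---|---|---|
| 1 | 1.25 | 0.190 | 0.38 |
| 2 | 2 | 0.241 | 0.48 |
| 4 | 5 | 0.381 | 0.75 |

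If every patient in an arm receives the same volume, volume and arm are the same variable and the lidocaine coefficient cannot be estimated.

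**Attenuation through a scale.** Assumed model: injection pain Y has within-arm SD 1 and arm effect b; the trait T has SD 1 and correlation rho with Y; the post-injection score is S = T + gY, where g is the feedback from pain to score.

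- Within-arm slope of Y on S: (rho + g)/(1 + 2g·rho + g²).
- Arm difference in S: g·b.
- Adjusted lidocaine coefficient: b × [1 − g(rho + g)/(1 + 2g·rho + g²)].

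With b = 0.50:

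- rho = 0, g = 0.2: 0.50 × (1 − 0.04/1.04) = 0.48
- rho = 0, g = 0.4: 0.50 × (1 − 0.16/1.16) = 0.43
- rho = 0.4, g = 0.2: 0.50 × (1 − 0.12/1.20) = 0.45
- rho = 0.4, g = 0.4: 0.50 × (1 − 0.32/1.48) = 0.39

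With g = 0 or b = 0 nothing is lost. The unadjusted difference stays at 0.50. For 4-hour pain, if it correlates 0.5 with injection pain, the whole effect passes through injection pain and rho = 0, a true 0.25 becomes 0.240 (g = 0.2) or 0.216 (g = 0.4).

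**Scale coefficients.** In the same model with rho = 0, simulated trials of 138 patients find the scale associated with injection pain at the two-sided 5% level in about 5%, 21%, 63% and 99% of runs for g = 0, 0.1, 0.2 and 0.4. The within-arm correlation is g/√(1 + g²), or about 0, 0.10, 0.20 and 0.37. The association is therefore real whenever g is above zero; only its direction is unknown.

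**The case against.** **The plan claims association, not direction.** This stands. A reader might take the 21%, 63% and 99% above as false-positive rates. They are not: the stated hypothesis concerns association, and in those scenarios an association exists. They would be errors only under a causal hypothesis that the plan does not state.

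**The feedback is assumed.** This also stands. The documents give no items, recall periods or data from which to judge whether one injection can move these scores, and zero feedback means no attenuation. Even the largest loss shown, 0.50 to 0.39, is smaller than the 0.34 half-width. No figure can be given for satisfaction or empathy, because the plan gives no SD or expected effect for them.

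**Joint entry is inferred, and so is the regression's role as sole source for satisfaction and empathy.** Both are readings: the first of the phrase about independent association, the second of a terse analysis sentence. The sponsor can settle both by specifying the models.

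**Volume has nothing to do with survey order.** True, but it is the same kind of fault, a variable that depends on treatment placed in the model for the treatment effect. It needs no assumption about feedback.

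**Asking the scales last protects the primary pain rating.** This is a fair defence of the order. A reader might infer that the scales must be moved before the injection; the documents do not support that as the necessary remedy.

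Two other listed responses are less clear. Pain over the last 7 days refers mostly to the time before the injection. Pain at 5 minutes may not precede the scales, since the survey itself takes 5 minutes.

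**Conclusion.** The point holds as a fault in how the secondary models are specified. If the listed variables enter together, the lidocaine coefficient for pain, satisfaction and empathy is adjusted for three post-injection scales and for a volume that lidocaine itself increases.

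The volume part rests on the plan's own statement that lidocaine adds volume. Its size, from 1.25-fold variance inflation to a coefficient that cannot be estimated, depends on volumes not given. The scale part is conditional on feedback and a real arm effect, and is modest over the assumed range. The scale associations with the immediate ratings can be reported, but not as evidence that the scales predict those ratings.

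A reader might infer that the trial's main result is compromised. It is not: the unpaired t-test on injection pain uses none of these variables, and the same holds for a t-test on 4-hour pain. The sample size reproduces.

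**What to change.** Specify in the Statistical analysis section:

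1. The lidocaine effect on pain, satisfaction and empathy comes from models without PCS-4, PHQ-2, PSEQ-2 and total volume. They are either unadjusted or adjusted only for variables fixed before randomisation, such as age, sex, prior steroid injection and diagnosis.
2. The scale associations are fitted in separate models and reported as concurrent. Any lidocaine coefficient in those models is not presented as the treatment effect.
3. The planned t-tests stay as they are.

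The cost is a few sentences and a second set of models. Data collection and patient burden do not change.

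A further option for the sponsor to weigh is to give the three scales after consent and before randomisation. This would fix the time order but split the 5-minute survey, and it may prime the primary pain rating, which the Background section links to expected pain. Priming that is equal in both arms could still compress a difference near the top of the scale. For a true difference of 0.50, SD 1, scores rounded and capped at 10, and means of 8.0 and 8.5, priming of 0, 0.5 or 1 point gives an observed difference of 0.48, 0.45 or 0.39. That would make non-inferiority easier to show. With means of 4.3 and 4.8, starting from the trigger-finger average cited in the Background section, it stays at 0.50.

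### Pain at 5 minutes has no named analysis, and the effect of lidocaine on satisfaction and empathy would come only from a regression coefficient that is not a clean randomised contrast

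*Combined protocol and SAP*

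**What the plan says.** Two hypotheses compare the arms. The primary one reads "There is a difference in pain intensity during injection (directly assessed after the injection) between patients receiving corticosteroid injections in combination with lidocaine", against the arm without it. The first secondary one reads "There is a difference in pain intensity 4 hours after injection between patients receiving corticosteroid injections in combination with lidocaine vs without lidocaine".

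The remaining hypothesis states that no factors, adding lidocaine among them, are "independently associated with pain intensity, satisfaction with the visit, and perceived empathy". The secondary aim matches it: "Secondarily, the aim of this study is to assess factors independently associated with pain intensity, satisfaction with the visit, and perceived empathy". Neither gives a time point for pain.

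Under Measured variables, the response variables include "Pain intensity 5 minutes after injection", satisfaction both directly after the visit and at 4 hours, and JSPPPE. The explanatory variables include lidocaine use (yes/no), total injection volume, PCS-4, PHQ-2 and PSEQ-2.

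The method line under Statistical analysis is "Unpaired t-test for hypothesis testing and MV linear regressions for other hypotheses". The Hypotheses section adds that "we will perform our other analyses based on superiority, without margins of non-inferiority", without naming an outcome or a test. A mean difference with a 95% CI is promised only in the power section, for the primary pain score.

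**The concern.** In a randomised trial the effect of treatment on an outcome is most safely taken from the difference between allocated arms, which needs no model. For four listed response variables the plan does not commit to that difference.

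For 5-minute pain, no analysis is named. It is the only listed score between the injection and 4 hours, and the Background says of lidocaine that "it is characterized by a rapid onset of action". Non-inferiority could be declared on the primary score with no stated arm comparison a few minutes later. Whether and how the 5-minute score is reported could then be decided after the data are seen.

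For satisfaction and JSPPPE, any statement about lidocaine would rest on a coefficient whose meaning depends on which covariates enter. No selection rule is given, and some candidates may be affected by the treatment.

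**Working it through.** **1. Coverage of the response variables.**

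| Response variable | Hypothesis comparing arms | Analysis the text points to |
|---|---|---|
| Pain during injection | Primary | Unpaired t-test, mean difference with 95% CI |
| Pain at 4 hours | Secondary | Unpaired t-test, on the natural reading |
| Pain at 5 minutes | None | None named; at most a regression on pain with no time point |
| Satisfaction, directly after visit | None | Multivariable regression |
| Satisfaction, 4 hours | None | Multivariable regression |
| JSPPPE | None | Multivariable regression |

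Pain in the last 7 days is left out, since it essentially describes pain before the injection.

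**2. What may enter the regression.**
- Total volume is an explanatory variable, and the Background says that adding lidocaine increases volume and that this might increase pain. Volume therefore lies on the path from treatment to outcome.
- The recruitment section places PCS-4, PHQ-2 and PSEQ-2 in the survey taken after the injection, following the pain item. Treatment could influence them; the documents do not show whether it does.
- Lidocaine enters as recorded use, not allocated arm. The two differ only if some patients do not receive their allocation; no rate is given.

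**3. The plan's own sample size.** Inputs from the power section: margin 0.5, SD 1, one-sided alpha 0.05, power 90%. Per group: 2 × (1.645 + 1.282)² × 1² / 0.5² = 68.5, rounded up to 69, so 138 in total. With loss, 138 × 1.05 = 144.9, or 145. The figures reproduce.

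**4. Precision of a plain arm comparison at 69 per group.**
- Standard error: SD × √(2/69) = 0.170 SD.
- 95% CI half-width: t(0.975, 136) × √(2/69) = 0.337 SD. That is 0.34 points at the plan's SD of 1, and 0.67 at an assumed SD of 2.
- Detectable difference, two-sided 0.05: (1.960 + 0.842) × 0.170 = 0.48 SD at 80% power; (1.960 + 1.282) × 0.170 = 0.55 SD at 90%.
- Power for 0.5 SD: Φ(0.5/0.170 − 1.960) = 84%.

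**5. Loss of precision from adjusting for volume.** With correlation r between lidocaine use and volume, the standard error is multiplied by 1/√(1 − r²). The documents do not give r, so a range is assumed. Residual SD is held fixed.

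| r | SE multiplier | Power for 0.5 SD |
|---|---|---|
| 0 | 1.00 | 84% |
| 0.5 | 1.15 | 72% |
| 0.7 | 1.40 | 55% |
| 0.8 | 1.67 | 42% |
| 0.9 | 2.29 | 25% |
| 0.95 | 3.20 | 15% |

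**6. A change in what is estimated.** The total effect is the direct effect plus (slope on volume × difference in volume). As an illustration with assumed values, take a direct effect of −0.5, a slope of 0.5 and a volume difference of 1 unit: the total is −0.5 + 0.5 × 1 = 0. Over 2,000 simulated trials of 69 per arm, the unadjusted difference averaged 0.00 (SE 0.17) and the volume-adjusted coefficient −0.50 (SE 0.33). The model answers a different question from the randomised comparison.

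**The case against.** A reader might infer that these outcomes get no randomised comparison at all. The documents do not support that. The third hypothesis expressly includes adding lidocaine as a factor, and the coefficient of a randomised factor adjusted only for baseline covariates is a legitimate arm comparison. A long list of non-randomised covariates is not itself a flaw. The problem is narrower: volume, the post-injection scales, and use in place of allocation.

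A reader might also infer that a t-test of 5-minute pain is ruled out, or that the primary score says nothing about the moments after injection. Neither follows. The main aim refers to pain without a time, and the method line could be stretched to further outcomes. The power section also describes the primary outcome as pain immediately after the injection. The test is unspecified, not excluded. Nor do the documents give an onset time for lidocaine, so they do not establish that 5 minutes is when its effect should peak.

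Two further objections carry weight. Regression suits the stated aim of finding associated factors, and nothing in the documents suggests that lidocaine should change perceived empathy. Limiting formal tests to two pain scores also contains multiplicity. Both support calling the added comparisons secondary and keeping the regressions. Neither supports reading a treatment effect from a model that may contain volume. Finally, the half-width in step 4 shows what the proposed analysis would deliver; it does not measure harm from the present plan.

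**Conclusion.** The point holds in this form: one listed response variable (5-minute pain) has no named analysis, and three (satisfaction at two times, JSPPPE) have only a regression whose lidocaine coefficient is not assured to estimate the randomised effect.

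The size depends on covariate choices that the plan leaves open. If only baseline covariates entered, and lidocaine were coded by allocation, the distortion would disappear and only the missing unadjusted contrast would remain. If volume enters, the standard error multiplier is 1.15 to 3.20 over the assumed range of r, and the coefficient drops whatever effect runs through volume. The direction and size of any distortion from the post-injection scales are unknown. SD 1 is the plan's figure for pain with lidocaine; no SD is given for satisfaction or JSPPPE, so precision for those is known only in SD units.

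This concerns secondary outcomes. The primary analysis and the sample size stand, but the change is worth making before the data are analysed.

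**What to change.** Add to the secondary analyses an unadjusted comparison by allocated arm for 5-minute pain, satisfaction at each listed time point and JSPPPE: unpaired t-test for superiority, with the mean difference and 95% CI. Do this by intention to treat, with the already planned per-protocol analysis alongside. State that the effect of lidocaine on these outcomes is taken from these comparisons, and report the 5-minute difference next to the primary result.

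Keep the multivariable regressions, with lidocaine retained, as exploratory analyses of associated factors. State the pain time point for each, and state that the lidocaine effect will not be read from a model containing volume or scales completed after the injection.

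The cost is wording plus four more secondary comparisons on variables already listed. Label them secondary, with no claim from an isolated p-value. One detail to confirm: the description of the 4-hour call mentions only pain, so it should also say that satisfaction is asked then. No extra patients are needed.
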